1.0 Background and Rationale

Hypofractionated radiotherapy, the delivery of higher dose per fraction with reduced number of treatment fractions, is a promising treatment option for many disease sites. Hypofractionated radiotherapy inherently requires a smaller patient setup margin which in turn necessitates the use of image guidance to alleviate the increased risk of geometric misses and deleterious clinical outcomes.

The main thrust of modern image guidance is to localize the soft tissue target and represents a major paradigm shift from the verification of bony landmarks. The predominant form of image guidance is on-board kilo-voltage cone beam CT (KV-CBCT). Although KV-CBCT is highly effective in improving accuracy of the patient setup prior to treatment, CBCT has two major deficiencies when applied to verify hypofractionated radiotherapy or radiosurgery.

First, KV-CBCT only provides a “snapshot” of patient anatomy at the time of imaging, but not during actual radiation delivery. Secondly, flat panel based KV-CBCT employed in radiation therapy is less than effective in discriminating a soft tissue target in a low contrast environment. Localization of abdominal lesions for hypofractionated treatment is challenging with KV-CBCT. Alternative imaging methods are needed. Ultrasound imaging is one of the important technologies that are capable of soft tissue localization in the abdomen. We have a commercially available ultrasound system in our department. This system has been predominantly used for prostate patients, localizing the prostate prior to treatment. Ultrasound imaging alone, however, suffers insufficient of field of view to visualize a proper patient position for radiotherapy.

2.0 Objectives

Purpose of this protocol is to investigate the feasibility of combining on-board CBCT with ultrasound imaging to overcome the shortcomings of CBCT or ultrasound imaging alone for imaging guided radiotherapy delivery. Specifically, we will investigate (a) whether the ultrasound imaging can enhance soft tissue tumor localization; (b) whether the presence of a passive arm is interfering radiation delivery during each treatment; (c) whether the presence of the ultrasound probe will affect the choice of radiation beams and degrade treatment plan quality.

3.0 Patient/Sample Selection

We will recruit a total of 30 patients, 30 with prostate cancer that will undergo external beam treatment at the Department of Radiation Oncology.

All patients undergoing radiation treatment for prostate cancer, with EBRT or SBRT are eligible.

A completed patient eligibility checklist is required following the approved standard operating procedure of the enrolling institution.

3.1 Inclusion Criteria

Patients must meet all of the following inclusion criteria to be eligible for enrollment:

_____ 3.1.1 The patient must have prostate cancer by biopsy, with the intent of undergoing definitive dose radiation therapy to targets within the prostate. Patients with prostatectomy receiving post-operative radiotherapy are also eligible.

_____ 3.1.2 Age > 18 years.

_____ 3.1.3 Performance status - Karnofsky PS \geq 70

_____ 3.1.4 Subjects must have the ability to understand and the willingness to sign a written informational form.

3.2 Exclusion Criteria

The presence of the following will exclude a patient from study enrollment.

_____ 3.2.1 Patients with uncontrolled inter-current illness or psychiatric illness/social situations that would limit compliance with study requirements.

4.0 Registration Procedures

All patients enrolled on study will be entered into the Oncore database

5.0 Research Plan

5.1 Investigate whether the ultrasound imaging can enhance soft tissue tumor localization.

(a) Following the standard clinical procedure, daily KV-CBCT image for each patient will be acquired and used to guide for patient setup prior to treatment delivery. Because of limited soft tissue contrast in KV-CBCT to observe the soft tissue organ, such as the prostate, the added ultrasound image may enhance soft tissue localization prior to treatment for these patients.

The ultrasound device will be calibrated to the treatment iso-center via an external camera system and infrared markers on the ultrasound (US) probe. A commercially available passive arm will be acquired and attached to the ultrasound probe. Following our current clinical protocol, the patient treatment position will be determined solely based the daily KV-CBCT. After KV-CBCT guidance, a pre-treatment US image will be acquired for the study but not used for patient positioning. The success of this specific aim is defined as that the tumors can be visualized in the ultrasound images in at least 80% of patients enrolled.

(b) Investigate whether the presence of a passive arm will interfere with radiation delivery during each treatment.

In order to monitor tumor or organ motion during radiation, the US probe will be placed using a passive arm, as shown in the figure below. This passive arm will be attached to the treatment couch and also in contact with the patient during the radiation. Although the passive arm is commercially available, we plan to test whether the presence of the US probe will interfere radiation delivery during each treatment. Specifically, we will test: (a) whether the passive arm reduces the clearance between the patient and the gantry of the linear accelerator; (b) whether the passive arm can hold a consistent contact pressure with the patient under normal breathing motion; (c) whether the passive arm can be automatically released if a patient makes a large movement. The success of this specific aim is defined as that at least 80% of patients are able have the ultrasound probe attached during the entire treatment course.

Figure 1.

(c) Investigate whether the presence of the ultrasound probe will interfere with the choice of radiation beams and degrade plan quality

The presence of the US probe and the passive arm may block the access of some radiation beams. The specific aim of this study to investigate whether altering the radiation beam directions will affect the treatment plan quality. Our preliminary planning data[1] showed that it is necessary to choose different radiation beam angles, but the impact on treatment plan quality is not clinically significant for most patients. Patients for whom treatment plan quality is in the opinion of the treating physician adversely impacted by alteration of beam angles required by presence of the US probe will be treated with the non-altered plan, and thus be included in step 5.1(a), but excluded from 5.1(b&c), as US probe will be removed prior to treatment in these cases to allow for treatment with the best possible plan. We expect this to be rare. The success of this specific aim is defined as that the quality of the plans for 80% of patients will not be affected in the presence of the

ultrasound probe, defined as no more than a 2% decrease in tumor coverage, and also no more than a 2% increase in the dose to the most critical normal tissue for that tumor location (Prostate: dose to hottest 10 cc of rectum.)

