6.0 Study Parameters

The study parameters collected are the US images acquired prior to each treatment and during radiation delivery. Pre-treatment KV-CBCT images will also be collected for dosimetric analysis. Specifically, the tumor location detected from combined US/KV-CBCT images will be compared with using KV-CBCT alone. Using the KV-CBCT the gold standard, 3D radiation dose distributions will be re-calculated according to the tumor localizations using KV-CBCT alone and using combined US/KV-CBCT. For SBRT prostate cancer, we will compare the following dosimetric endpoints, extracted from dose volume histograms.

Organ Name	Endpoint 1	Constraints
PTV_HD*	V5000 cGy	> 50%
PTV_LD*	V3625 cGy	> 95%
PROSTATE	V3625 cGy	> 95%
BLADDER	D0.03 cc	< 5250 cGy
RECTUM_ANT	D0.03 cc	<5000 cGy
RECTUM_LAT	D3cc	< 4000 cGy
RECTUM_POST	V0.03 cc	< 2250 cGy
URETHRA	V0.03cc	< 5000 cGy
URETHRA	D1cc	< 4500 cGy

PTV_HD = planning target volume in high dose prescription dose of 5000 cGy

PTV_LD = planning target volume in low prescription dose of 3625 c Gy.

For patients treated with conventional multiple fractionation, we will compared the following dosimetric endpoints, extracted from dose volume histograms.

Organ Name	Endpoint 1	Constraints	Planned	comments
CTV_7800	V7800 cGy	> 99%		
PTV_7800	V7800 cGy	> 95%		
BLADDER	V7000 cGy	< 10%		
BLADDER	V6000 cGy	< 20%		
RECTUM	V7000 cGy	< 10%		
RECTUM	D10cc	< 7000 cGy		
RECTUM	V5000 cGy	< 30%		Without pelvic nodes
RECTUM	V5000 cGy	< 50%		With pelvic nodes
FEMORAL HEAD_L	V5000 cGy	< 5%		
FEMORAL HEAD_R	V5000 cGy	< 5%		
PENILE BULB	Dmean	< 5250 cGy		

For patients with prostatectomy receiving post-operative radiotherapy with conventional multiple fractionation, we will compared the following dosimetric endpoints, extracted from dose volume histograms.

Organ Name	Endpoint 1	Constraints	Planned	comments
CTV_7000	V7000 cGy	> 99%		
PTV_7000	V7000 cGy	> 95%		
BLADDER	V6500 cGy	< 40%		
BLADDER	V4000 cGy	< 60%		
RECTUM	V6300 cGy	< 10 %		
RECTUM	D10 cc	<6300 cGy		

RECTUM	V4500 cGy	< 30 %		Without Pelvic nodes
RECTUM	V4500 cGy	< 50%		With pelvic nodes
FEMORAL HEAD_L	V5000 cGy	< 5%		
FEMORAL HEAD_R	V5000 cGy	< 5%		
PENILE BULB	Dmean cGy	< 5250 cGy		

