8.8 Importance of the knowledge to be gained

The research aims to develop a novel non-invasive approach of image guidance of hypofractionated SBRT of patients with abdominal and pelvic tumors with the capability of continuous monitoring during radiation delivery. Successful monitoring of target position during treatment is expected to reduce margins required during radiation treatment, and thereby reduce dose to surrounding normal tissue. This has been demonstrated clinically using real-time tracking technology using implanted markers in prostate cancer, but in this study would be able to be done non-invasively using ultrasound.

The analysis of the recalculated dosimetry will show the uncertainty of dose delivery using current CBCT and ultrasound image guidance methods and shed light on the degree of improvement that can be achieved when they are combined. The data from the feasibility studies will be immensely useful for designing a treatment protocol with adequate statistical power to prove the improvement in treatment accuracy and efficacy. In turn, a cost-benefit analysis can then be made in terms of resource allocation, treatment efficiency and margin reduction. The information will be most significant as a baseline for assessing the cost-effectiveness of the next generation of advanced IGRT machines such as those employing on-board MRI.

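### The section 6.0 CBCT-to-ultrasound difference includes target motion, and possibly probe displacement, so it cannot be read as a localization gain

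*Combined protocol and SAP*

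**What the plan says.** Section 5.1(a) sets the sequence. CBCT comes first, as in routine care: "Following the standard clinical procedure, daily KV-CBCT image for each patient will be acquired". It alone fixes the set-up, since "the patient treatment position will be determined solely based the daily KV-CBCT". The study image follows: "After KV-CBCT guidance, a pre-treatment US image will be acquired for the study but not used for patient positioning".

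Section 5.1(b) describes a probe held against the patient by a passive arm, and one of its tests is "whether the passive arm can hold a consistent contact pressure with the patient under normal breathing motion". The purpose of the arm is given there as well: "In order to monitor tumor or organ motion during radiation, the US probe will be placed using a passive arm".

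Section 6.0 compares the tumor location from the combined images with that from CBCT alone, and says that "3D radiation dose distributions will be re-calculated according to the tumor localizations using KV-CBCT alone and using combined US/KV-CBCT". Section 8.8 expects the recalculated dosimetry to "shed light on the degree of improvement that can be achieved when they are combined".

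The plan does not state the probe state at CBCT, the interval between the two images, or how they are combined into one location. Section 7.0 calls the analysis primarily descriptive.

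**The concern.** Objective (a) in section 2.0 asks whether ultrasound improves localization of the soft-tissue target. The success criterion for that aim, visualization in at least 80% of patients, shows that the tumor can be seen. It does not show that it is located better. The location and dose comparison in 6.0 is the only planned analysis that bears on better localization.

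That comparison sets an earlier image against a later one taken with a probe in contact. If the whole difference is credited to localization, motion between the images, and possibly a shift caused by the probe, would be counted as a gain from ultrasound or an error of CBCT. Section 8.8 also says the data will help to design a later, adequately powered protocol, which could then start from a wrong effect size.

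**Working it through.** The plan states no figure on this point, so there is none to reproduce. The check is whether the planned data can isolate the localization difference, followed by an illustration of scale.

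**Step 1. What is observed.** For one fraction, write the ultrasound-minus-CBCT difference as D = L + M + P, where
- L is the localization difference between the two methods,
- M is target motion between the two images,
- P is displacement of the target by the probe, relative to its state at CBCT.

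**Step 2. Do the documents allow M and P to be non-zero?**
- M: yes. The Background says CBCT gives a snapshot "of patient anatomy at the time of imaging, but not during actual radiation delivery", and 5.1(b) places the probe in order to follow motion. The study presumes that the target moves.
- P: conditionally. CBCT under the standard procedure, with the study ultrasound acquired afterwards, most naturally means no probe at CBCT, but no section says so. If the probe is absent at CBCT, D = L + M + P. If it is already in place, P largely cancels and D is about L + M. M remains in both cases.

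**Step 3. Can the plan separate them?** The pre-treatment pairing gives one D per fraction. Sections 5.1, 6.0 and 7.0 provide no CBCT repeated with the probe in place, no record of the interval or of the probe state, no independent reference position and no analysis by source. L is therefore not identified. Exchanging which of the two images serves as the reference does not help, because the same D is involved.

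**Step 4. Scale (assumed SDs, none from the documents).** Suppose L = 0 and M + P is normal with mean zero and SD s on each of three independent axes. The mean vector length is 2s√(2/π) = 1.596s.

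| Assumed s (mm) | Mean length of raw vector (mm) |
|---|---|
| 1 | 1.6 |
| 2 | 3.2 |
| 3 | 4.8 |

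Alternatively, suppose L has SD 2 mm and is independent of M + P. Its share of the variance of D is 2²/(2² + SD²), with SD that of M + P:

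| Assumed SD of M + P (mm) | Share of variance due to L |
|---|---|
| 1 | 4/5 = 80% |
| 2 | 4/8 = 50% |
| 3 | 4/13 = 31% |

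These figures describe the raw ultrasound-minus-CBCT vector. Section 6.0 uses a combined location whose rule is undefined, so the difference entering the dose recalculation may be smaller. No effect on a dose endpoint can be computed from the documents. If the probe shifts the target in a consistent direction, P has a non-zero mean that averaging over fractions or over the 30 patients does not remove.

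**The case against.** The strongest reply is that the study is not built on this comparison. Aim (a) succeeds on visualization, and the four measures in 7.0 are image adequacy, tracking, plan quality and adverse events. None uses the CBCT-to-ultrasound difference. Section 8.8 is cautious significance text and leaves proof of improvement to a later protocol. This stands, and it limits the point to interpretation of a secondary, descriptive result.

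Second, motion after CBCT is partly what the study wants to capture. The Background names the snapshot limitation as a deficiency of CBCT, and 8.8 ties the benefit to monitoring during delivery. This also stands: M is not pure nuisance. But knowing where the target is later is a different gain from locating it better at a given moment, and 6.0 does not say which of the two it reports.

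Three stronger readings are tempting and not supported.
- A reader might infer that probe displacement is certainly in the difference. The documents do not state the probe state at CBCT, so it is conditional.
- A reader might blame the fixed image order. Varying it would not remove displacement, because contact always accompanies ultrasound, and it would not change the random-motion figure above. CBCT first also follows from positioning on CBCT alone. What is missing is a paired reference in the same state.
- A reader might take the 1.6 to 4.8 mm as an expected error in this trial. It rests on assumed SDs and on the raw vector.

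**Conclusion.** The point holds as a limit on interpretation. Followed as written, the location and dose differences in 6.0 cannot be read as the localization gain for objective (a), or as the improvement that 8.8 hopes to show. They are between-image differences that include target motion and, if the probe was absent at CBCT, displacement by the probe.

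The conclusion needs only that the ultrasound is later and that the target can move, both of which the plan states or presumes. The probe part rests on an unstated condition. The size is unknown, and the figures above are illustrative only. A reader might infer that the trial's success criteria are compromised; they are not, since none uses this comparison. This is a cheap improvement, not a defect in the feasibility aims.

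**What to change.** 1. For each fraction, record the CBCT and ultrasound acquisition times and whether the probe was in contact at CBCT. Report the 6.0 location and dose differences by probe state and by time interval.
2. In 6.0 and 8.8, describe the result as a between-image difference that includes motion and, where applicable, probe displacement. Attribute it to localization only for fractions imaged in the same probe state and close in time, accepting that there may be few or none.
3. Beside it, report drift from the pre-treatment and during-delivery ultrasound series as a rough guide to the size of motion. Do not subtract it: it covers a different interval from CBCT to first ultrasound and does not estimate probe displacement. It is unavailable for patients whose probe is removed before treatment under 5.1(c).
4. Reconcile the sections on which probe state the CBCT-based set-up refers to, since patients under aim (b) are treated with the probe in contact. Which state applies is for the investigators to settle.

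The cost is protocol wording, two recorded items per fraction (the image times and the probe state) and a descriptive summary of images already collected. No extra imaging or patients are needed. The downside is a weaker improvement claim.

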7.0 Statistical Considerations

Because of limited funding from NIH, the number of patients that are planned to be enrolled into this protocol will be small and potentially lacking of the statistical power. The primary purpose of this study is a feasibility study to test whether a combined CBCT and ultrasound image guidance is clinically feasible. Our analysis is primarily descriptive and does not require any advanced statistics to analyze the endpoints. As a measure of protocol success we expect that:

- 1) Over 80% of patients have ultrasound images which are clinically adequate for treatment set-up in the judgment of the treating physician.
- 2) Over 80% of patients are able to undergo ultrasound based tumor tracking during treatment.
- 3) The quality of treatment plans for more than 80% of patients will not be affected.
- 4) No adverse events related to the ultrasound probe are noted during treatment.

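### Aim (a) asks whether ultrasound enhances localization, but its success rule counts ultrasound visualization alone, so it can be met when ultrasound adds nothing to KV-CBCT.

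*Combined protocol and SAP*

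**What the plan says.** Section 2.0 of the combined protocol and SAP gives objective (a) as "whether the ultrasound imaging can enhance soft tissue tumor localization", and the heading of section 5.1 repeats the question. The reason given in 5.1(a) is the limited soft tissue contrast of KV-CBCT, so CBCT is what ultrasound is meant to improve on.

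Success in 5.1(a) is "defined as that the tumors can be visualized in the ultrasound images in at least 80% of patients enrolled". The matching item in section 7.0 reads: "Over 80% of patients have ultrasound images which are clinically adequate for treatment set-up in the judgment of the treating physician". Neither mentions CBCT.

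Both images are available in the same patients. Under 5.1(a), a "daily KV-CBCT image for each patient will be acquired and used to guide for patient setup prior to treatment delivery", and a pre-treatment ultrasound image follows, for study use only.

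Section 6.0 states that "the tumor location detected from combined US/KV-CBCT images will be compared with using KV-CBCT alone". The next sentence begins "Using the KV-CBCT the gold standard, 3D radiation dose distributions will be re-calculated" and applies this to the localizations from each method. No size of difference is named as an improvement, and the comparison is not listed among the success criteria in section 5.1 or 7.0.

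On size and method, the plan says "We will recruit a total of 30 patients", and section 7.0 describes the study as a feasibility study with mainly descriptive analysis.

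**The concern.** To enhance localization means to do better with ultrasound than without it. The rule instead measures how often ultrasound shows the target, and the answer to that does not depend on what CBCT shows in the same patient. A report that follows the plan could state that aim (a) succeeded, and a reader would take this to mean that ultrasound improved on CBCT, although the rule never tested it.

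This matters beyond the present study. Section 8.8 says the data will help design a later, adequately powered trial of improvement. If that trial used a paired comparison of visibility, it would need the proportion of patients in whom ultrasound shows the target and CBCT does not. A rate for ultrasound alone cannot supply that figure.

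**Working it through.** The plan gives no sample-size derivation, alpha, power, or visualization rate for either method, so there is no stated figure to reproduce. All rates below are assumptions.

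**Step 1: the rule as a count.** With n = 30 (section 3.0), 0.80 × 30 = 24. At least 80% (5.1(a)) means 24 or more patients. Over 80% (section 7.0) means 25 or more. The endpoints also differ: visualized in one, adequate for set-up in the other.

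**Step 2: what the rule depends on.** Let p be the true ultrasound visualization rate. The chance of meeting the rule is the binomial tail, the sum over k from r to 30 of C(30,k) p^k (1−p)^(30−k), with r = 24 or 25.

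| Assumed p | r = 24 | r = 25 |
|---|---|---|
| 0.70 | 0.160 | 0.077 |
| 0.80 | 0.607 | 0.428 |
| 0.85 | 0.847 | 0.711 |
| 0.90 | 0.974 | 0.927 |
| 0.95 | 0.999 | 0.997 |

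No CBCT quantity enters. At p = 0.90 the 5.1(a) rule is met with probability about 97%, even if CBCT shows the target in every patient in whom ultrasound does.

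**Step 3: what enhancement would depend on.** Classify each patient by whether the target is visible on both images (a), on ultrasound only (b), on CBCT only (c), or on neither (d), with a + b + c + d = 30. The rule uses a + b. On a visibility scale, the patients gained by adding ultrasound are b. If a + b = 25, b can be anything from 0 to 25 and the result of the rule is the same.

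| Assumed case | Both | US only | CBCT only | Neither | US total | Rule | Gain from US |
|---|---|---|---|---|---|---|---|
| 1: CBCT 27/30, containing all US-visible patients | 25 | 0 | 2 | 3 | 25 | met | 0/30 |
| 2: CBCT 24/30, US shows all 6 others | 14 | 6 | 10 | 0 | 20 | not met | 6/30 = 20% |

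Case 1 uses 25 so that it clears both counts in Step 1. In case 2 the exact (Clopper-Pearson) 95% interval for 6/30 is 7.7% to 38.6%. In case 1 the upper limit for 0/30 is 1 − 0.025^(1/30) = 11.6%.

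**Step 4: whether section 6.0 fills the gap.** Its location comparison is the right kind of comparison, but it has no threshold and no link to success. Its dose recalculation takes KV-CBCT as the reference. Where the two localizations differ, the dose difference then reads as a departure from CBCT. That part cannot by itself show that the ultrasound-aided position was the better one.

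**The case against.** The strongest reply is that this is a feasibility study and says so. Section 2.0 opens with feasibility, section 7.0 concedes limited power, and section 8.8 leaves proof of improvement to a later protocol. A visualization rate is a normal feasibility endpoint. That stands, and nothing here calls for a test, a power calculation or more patients. It does not remove the mismatch between the endpoint and the question it is said to answer.

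A reader might go further and infer that the protocol has no CBCT comparator at all. The documents do not support that, because section 6.0 plans one. Nor does the gold-standard phrase clearly cover all of section 6.0. It opens the sentence on dose recalculation, while the location comparison is in the sentence before.

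A reader might also infer that success is almost assured, because section 1.0 says of the ultrasound system: "This system has been predominantly used for prostate patients, localizing the prostate prior to treatment". That reports use, not a visualization rate, and section 3.1.1 also admits post-prostatectomy patients, to whom such experience may not carry over.

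Paired scoring has limits of its own. Patients are positioned on the CBCT, so a question whether it is adequate for set-up may be answered yes almost every time. Visibility is also not accuracy: both images may show the target while one places it better. These points stand and shape the fix.

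**Conclusion.** The point holds for the success rule. Neither the 5.1(a) rule nor the section 7.0 criterion contains a KV-CBCT term, so meeting either does not answer objective (a). Section 6.0 does not repair this as written.

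The cases in Step 3 show that the rule can be met with 0 of 30 patients gained, or failed with 6 of 30 gained. They rest on assumed rates and treat visibility as the measure of gain. They show what the rule permits; a reader should not infer that the rule will mislead in this trial, because the documents give no visualization rate for either method.

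Patient positioning is unaffected, since it follows CBCT alone. What changes is the conclusion that may be drawn for aim (a). The protocol should be amended, but the fault does not undermine the trial as a feasibility study.

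**What to change.** 1. State in 5.1(a) and 7.0 that the 80% rate is a technical feasibility criterion for ultrasound visualization, and that meeting it does not support a conclusion of enhancement. Use one endpoint and one cut-off in both places. This is a change of wording only.

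2. Describe enhancement within patient. Score target visibility on the same-fraction CBCT before the ultrasound image is viewed, using the same item as for ultrasound. Ask about visibility of the target, not adequacy of the CBCT for set-up. Since imaging is repeated over the treatment course, name in advance either the fraction to be scored or the per-patient summary.

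3. Report the paired 2×2 table with the ultrasound-only proportion and its exact 95% interval, beside the section 6.0 location differences. Visibility is a partial measure of localization accuracy and should not be the only evidence. State that the section 6.0 dose comparison, with KV-CBCT as reference, cannot by itself show that ultrasound is better.

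The cost is some scoring time and the need to read CBCT first, which matches the order of acquisition. No further imaging or patients are needed. The documents do not say that the treating physician already reviews both images, so the reading time should be counted as new work.

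### Aim (b) is judged only by a pooled whole-course proportion, so its 80% result can depend on the regimen mix as well as on probe performance

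*Combined protocol and SAP*

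**What the plan says.** All references are to the combined protocol and SAP.

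- **Question.** Section 2.0 and the opening of 5.1(b) put the question session by session: does the arm or probe interfere with delivery at each treatment?
- **Criterion.** Section 5.1(b) calls the aim successful if "at least 80% of patients are able have the ultrasound probe attached during the entire treatment course". The unit is the patient and the period is the whole course.
- **Second statement.** Section 7.0 words it differently: "Over 80% of patients are able to undergo ultrasound based tumor tracking during treatment".
- **Cohort.** Section 3.0: "We will recruit a total of 30 patients", and "All patients undergoing radiation treatment for prostate cancer, with EBRT or SBRT are eligible". Section 3.1.1 adds: "Patients with prostatectomy receiving post-operative radiotherapy are also eligible". No quota, target mix or stratification is given.
- **Regimens.** Section 6.0 has separate dosimetric tables for SBRT ("For SBRT prostate cancer, we will compare the following dosimetric endpoints"), for conventional courses ("For patients treated with conventional multiple fractionation") and for post-operative conventional courses. Aim (b) has no such split.
- **Data.** Section 6.0: "The study parameters collected are the US images acquired prior to each treatment and during radiation delivery". For attachment itself, Section 8.2 plans only the number of patients with the probe attached and the number with it removed.

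**The concern.** The question concerns a session, while the criterion cumulates over a course. Course length differs by regimen in kind even though no fraction counts appear: Section 1.0 defines hypofractionation by its reduced number of fractions, Section 8.8 describes SBRT as hypofractionated, and Section 6.0 sets conventional multiple fractionation apart from SBRT. With equal reliability per session, a longer course leaves fewer patients with an unbroken record.

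Two things follow. First, the pooled proportion mixes course length with probe performance, and the plan has no means of separating them. Second, counts of patients attached and removed do not distinguish a patient who missed one fraction from one who never tolerated the probe.

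Section 8.8 says that the results will inform a later, adequately powered protocol, and it names hypofractionated SBRT as the target. A pooled figure below 80% could come from long courses alone, and one above 80% could come from short courses alone. The designers of the next protocol could not tell which.

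**Working it through.** **The plan's own figure.** 0.80 × 30 = 24, so at least 80% means 24 of 30 and over 80% means 25 of 30. The documents give no derivation, expected rate, alpha or power to reproduce. Section 5.1(c) also drops patients with degraded plans from aim (b), so the denominator may be below 30.

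**Assumed inputs (not in the documents).** SBRT 5 fractions. Conventional 39 fractions (7800 cGy ÷ an assumed 200 cGy), with 20 as a low alternative. Per-fraction attachment probability q = 0.98 to 0.998, equal in both regimens. Within-patient correlation ρ = 0 to 0.3.

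**Formulas.** With independent fractions, the chance that a patient keeps the probe for all n fractions is qⁿ. With correlation, use a beta-binomial: with s = (1 − ρ)/ρ, the chance is the product over i = 0, …, n − 1 of (qs + i)/(s + i).

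**Whole-course success**

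| q | ρ | Conventional n | SBRT (n = 5) | Conventional | Gap, points |
|---|---|---|---|---|---|
| 0.99 | 0 | 39 | 0.951 | 0.676 | 27.5 |
| 0.99 | 0 | 20 | 0.951 | 0.818 | 13.3 |
| 0.99 | 0.1 | 39 | 0.959 | 0.856 | 10.3 |
| 0.99 | 0.3 | 39 | 0.970 | 0.930 | 4.0 |
| 0.98 | 0.1 | 39 | 0.920 | 0.733 | 18.7 |
| 0.998 | 0 | 39 | 0.990 | 0.925 | 6.5 |

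For a whole-course rate of 80% under independence, q must be 0.8^(1/5) = 0.956 for 5 fractions, 0.8^(1/20) = 0.989 for 20 and 0.8^(1/39) = 0.994 for 39.

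**Expected pooled rate by mix (SBRT/conventional), 5 v 39 fractions**

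- q = 0.99, ρ = 0: 20/10 gives (20 × 0.951 + 10 × 0.676)/30 = 0.859; 10/20 gives (10 × 0.951 + 20 × 0.676)/30 = 0.768 (0.767 before rounding the inputs).
- q = 0.99, ρ = 0.1: (20 × 0.9591 + 10 × 0.8562)/30 = 0.9248; (10 × 0.9591 + 20 × 0.8562)/30 = 0.8905.
- q = 0.98, ρ = 0.1: 0.857 and 0.795.

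With 20 conventional fractions, q = 0.99 and ρ = 0, the two mixes give 0.907 and 0.862.

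**Probability of at least 24 of 30 (exact sum of two binomials), 5 v 39 fractions**

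| q | ρ | All SBRT | 15/15 | All conventional |
|---|---|---|---|---|
| 0.99 | 0 | 0.999 | 0.685 | 0.101 |
| 0.98 | 0.1 | 0.991 | 0.747 | 0.272 |
| 0.98 | 0.3 | 0.998 | 0.979 | 0.900 |
| 0.998 | 0 | 1.000 | 1.000 | 0.994 |

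The mix matters a great deal in some rows and hardly at all in others. In every row the result also depends on q.

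**The case against.** A reader might infer that the 80% verdict is decided by regimen mix rather than by the device. The documents do not support that. They give no fraction counts, mix or removal rates, and per-fraction performance drives the result in every scenario. The contrast of 85.9% with 76.7%, on either side of 80%, needs 39 fractions, 99% success and independence together. With correlation 0.1, or with 20 conventional fractions, both mixes exceed 80%. Independence is doubtful, since body habitus and tolerance of probe pressure plausibly persist within a patient. An expected rate is also not a verdict: under independence the 10/20 mix still reaches 24 of 30 with probability 0.43, and the 20/10 mix with 0.90.

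Whole-course attachment is a legitimate feasibility measure. A device lost more often over a long course is less feasible there, and a per-fraction average alone could hide patients who never tolerate the probe. Section 7.0 calls the analysis descriptive, and nothing forbids reporting by regimen. The wording about being able to have the probe attached, together with 7.0's looser statement, also leaves room for a reading in which one incidental miss is not a failure.

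All of this stands, and it argues against replacing the criterion. It does not remove the gap. The per-session question has no per-session measure, the planned attachment record cannot supply one, and the four success statements in 7.0 are the plan's only formal yardstick. The session images in 6.0 might allow partial reconstruction, but the plan does not say they will be used so, and a pre-treatment image does not show that the probe stayed on.

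**Conclusion.** The point holds in a limited form. As written, aim (b) cannot answer its own per-session question, and its pooled 80% result can depend on regimen mix as well as on probe performance. That much follows from the text and needs no assumption beyond SBRT courses being shorter.

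The size does rest on assumptions. The difference in whole-course success between regimens runs from about 27 points (5 v 39 fractions, 99% per fraction, independence) to about 4 points (correlation 0.3). It matters little for the verdict at 99.8% per-fraction success or when removal is mainly a lasting patient trait. At 98% and correlation 0.1 it still moves the chance of passing from 0.991 (all SBRT) to 0.272 (all conventional). The result would be hard to interpret or carry forward unless it is also reported by regimen and per fraction.

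**What to change.** Keep the whole-course 80% criterion and add to it.

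1. **Section 8.2:** record the probe as attached or removed at each fraction.
2. **Sections 5.1(b) and 7.0:** report beside the criterion (i) the whole-course proportion separately for SBRT, conventional and post-operative patients; and (ii) for each patient, the proportion of delivered fractions with the probe in place throughout, averaged over patients, overall and by regimen, with a confidence interval that takes the patient as the unit.
3. **Same edit:** reconcile 5.1(b) with 7.0. One requires at least 80% (24 of 30) over the entire course; the other requires over 80% (25 of 30) during treatment. State the denominator after the exclusions described in 5.1(c).

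The cost is one extra entry per fraction and some wording; no added patients or procedures. The regimen strata will be small and should be labelled descriptive: 8 of 10 has a 95% Clopper-Pearson interval of 44.4% to 97.5%, and even the pooled 24 of 30 has 61.4% to 92.3%.
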